6.1.4. Supportive Care

Patients will receive supportive care for acute or chronic toxicity, including blood components or antibiotics, and other intervention as appropriate and as per institutional guidelines.

6.2. Preparation/Handling/Storage/Accountability

The investigator or designee must confirm appropriate conditions have been maintained for all MT-401 received and any discrepancies are reported and resolved before use of the MT-401.

Only patients enrolled in the study may receive MT-401. All MT-401 must be stored in a secure, environmentally controlled, and monitored (manual or automated) area in accordance with the labeled storage conditions.

The investigator or designee is responsible for MT-401 accountability, reconciliation, and record maintenance (i.e., receipt, reconciliation, and final disposition records).

Further guidance and information for the final disposition of unused study investigational product are provided in the Investigational Product Manual.

6.3. Randomization

Disease assessment and group assignment occur at Day 80 ± 0 (± 5 days) post-HCST, prior to randomization for Group 1 patients. Post-transplant baseline MRD testing will be performed centrally, and results must be available prior to randomization.

For Group 1, randomization codes will be prepared to allow the clinical study sites to enroll patients by using an interactive response technology (IRT) system. Treatment group assignments will be known to site personnel (i.e., investigator, pharmacist, and study staff) and patients. After completion of required screening procedures, patients will be assigned, using the randomization schedule, to MT-401 vs observation (SoC) with a 1:1 allocation. The randomization schedule will be created with two stratification factors as specified in Section 4.1 using random block sizes. SoC patients in Group 1-Arm B who relapse after randomization may cross over to Group 2 to receive MT-401, if the subgroup is open and/or Sponsor agreement.

For Group 2, after the patient's eligibility is established and informed consent has been obtained, the patient will be enrolled, and a number will be assigned through the IRT. Since this is a single-arm cohort, all enrolled patients who meet eligibility criteria will be treated with MT-401.

Due to the nature of the administration of MT-401 along with the fact that the endpoints are objectively evaluated without the concern for bias, the study is not blinded.

Patients in the Safety Lead-in (Cohorts I and II) and Cohorts III-V will not be randomized.

Confidential Page 39 of 74

6.4. Study Intervention Compliance

When patients are dosed at the site, they will receive MT-401 directly from the physician or trained personnel, under medical supervision. The date and time of each dose administered in the clinic will be recorded in the source documents and recorded in the electronic case report form (eCRF). The dose of MT-401 and study patient identification will be confirmed at the time of dosing by a member of the study site staff other than the person administering the MT-401.

6.5. Concomitant Medications

Any medication or vaccine (including over-the-counter or prescription medicines, vitamins, and/or herbal supplements) that the patient is receiving at the time of enrollment or receives during the study must be recorded along with:

- Reason for use
- Dates of administration including start and end dates
- Dosage information including dose and frequency

The Medical Monitor should be contacted if there are any questions regarding concomitant or prior therapy.

6.5.1. Prohibited Concomitant Medications

Patients should not receive other antineoplastic agents or systemic steroids. Physiologic doses of systemic steroids (e.g., for adrenocortical insufficiency) are allowed before or after MT-401. For patients in Group 2, bridging therapy prior to MT-401 infusion is permitted as described in eligibility.

If steroids are received outside parameters specified in protocol, the patient may be considered unevaluable.

Patients should not be administered any live vaccines while on study unless prior approval from Sponsor is obtained.

6.5.2. Toxicity Management

The study site will supply rescue medication that will be obtained locally. The following rescue medications may be used to manage toxicity, as explained in Section 11.1.2:

- 1. Corticosteroids (oral or IV)
- 2. Tocilizumab

Although the use of rescue medications is allowable, the use of rescue medications should be delayed, if no safety concerns related to study drug are present, for at least 6 months following the administration of MT-401. The date and time of rescue medication administration as well as the name and dosage regimen of the rescue medication must be recorded.

Confidential Page 40 of 74

6.6. Dose Modification

No dose modifications will be allowed except in rare instances of manufacturing constraints, and any other issues specifically discussed with the Sponsor. As a result, patients may receive either lower or higher than the intended doses; these patients will complete the study but will be evaluable in a separate sub-group.

Timing of MT-401 administration (at least 2 weeks apart) may be modified for 1 week due to inclement weather, vacation, etc., but any longer durations need to be discussed with the Sponsor. Administration of MT-401 can also be delayed due to management of AEs or other toxicities, but patients should resume T cell infusions within 2 weeks of their scheduled dose. If greater than 2 weeks is needed, Sponsor will determine if patient can resume T cells infusions. All dose modifications should be documented, including the approach taken and a clear rationale for the need for modification. Additionally, the investigator must assess if a toxicity is considered attributable to T cells. If MT-401 is available for a patient, a patient may be re-dosed if requested by the investigator and approved by the Sponsor on a case-by-case basis.

7. DISCONTINUATION OF MT-401 AND PARTICIPANT DISCONTINUATION/WITHDRAWAL

7.1. Discontinuation of MT-401

If it becomes necessary for a patient to permanently discontinue MT-401, the patient will remain in the study to be evaluated for safety, response, and survival. See the SoA (Table 1) for data to be collected at the time of intervention discontinuation and follow-up and for any further evaluations that need to be completed.

The following criteria will result in the patient being ineligible for further treatment on the protocol, although safety and response data will continue to be collected as applicable:

- Any patient who develops a DLT. In such patients, the toxicity will be followed until resolution or until their off-study date.
- Any patient who receives any other hematopoietic cell product (e.g., donor leukocyte infusion) except for routine blood product transfusions such as platelets and packed red blood cells. In such patients, AE data collection will cease.
- Any patient who enrolls in another clinical study involving investigational product or other type of medical research judged not to be scientifically/medically compatible with this study or receives antineoplastic treatment for relapse of their primary malignancy within 4 weeks after the T cell infusion. In such patients, adverse event data collection will cease.
- Refusal of the patient to continue treatment or observations.
- Decision by the investigator that discontinuation of treatment is in the patient's best medical interest
- Unrelated medical illness or complication deemed significant by the investigator.

• Death.

Confidential Page 41 of 74

- Progressive Disease.
- Lost to follow-up.
- At the request of Marker Therapeutics, Inc.
- Any patient who becomes pregnant.

Any new clinically relevant finding should be reported as an AE.

7.2. Participant Discontinuation or Withdrawal from the Study

A patient may withdraw from the study at any time at his/her own request or may be withdrawn at any time at the discretion of the investigator for safety, behavioral, compliance, or administrative reasons. This is expected to be uncommon. Patient may agree to be followed for safety, efficacy, and survival after discontinuation from the study.

At the time of discontinuing from the study, if possible, an early discontinuation visit should be conducted (as described in the SoA [Table 1]). The patient will be permanently discontinued both from MT-401 and from the study at that time (see Section 7.1 for details on MT-401 discontinuation).

If the patient withdraws consent for disclosure of future information, the Sponsor may retain and continue to use any data collected before such a withdrawal of consent. If a patient withdraws from the study, he/she may request destruction of any samples taken and not tested, and the investigator must document this in the site study records.

A patient will be considered off study when one of the following has occurred:

- The patient reaches End of Study, as defined in Section 4.4.
- If the patient desires to withdraw from the study or if the physician feels that it is in the best interest of the patient.
- Lost to follow-up (see Section 7.3 for details).
- Death.

7.3. Lost to Follow up

A patient will be considered lost to follow up if he or she repeatedly fails to return for scheduled visits and is unable to be contacted by the study site. Methods to account for missing data resulting for patients who were lost to follow up is described in the statistical analysis plan (SAP).

The following actions must be taken if a patient fails to return to the clinic for a required study visit:

- The site must attempt to contact the patient or the referring physician and reschedule the missed visit as soon as possible and counsel the patient on the importance of maintaining the assigned visit schedule and ascertain whether or not the patient wishes to and/or should continue in the study.
- Before a patient is deemed lost to follow up, the investigator or designee must make every effort to regain contact with the patient (where possible 3 attempts via at least 2 modalities [i.e., telephone call,

Confidential Page 42 of 74

e-mail, or a certified letter to the patient's last known mailing address or local equivalent methods]). These contact attempts should be documented in the patient's medical record.

• Should the patient continue to be unreachable after 3 attempts, the investigator may consider the patient withdrawn from the study.

Discontinuation of specific sites or of the study are handled as part of Section 10.6.

8. STUDY ASSESSMENTS AND PROCEDURES

Study procedures and their timing are summarized in the SoA (Table 1). Protocol waivers or exemptions are not allowed.

Safety concerns should be discussed with the Sponsor immediately upon occurrence or awareness to determine if the patient should continue or discontinue MT-401.

Adherence to the study design requirements, including those specified in the SoA, is essential and required for study conduct.

All screening evaluations must be completed and reviewed to confirm that potential patients meet all eligibility criteria. The investigator will maintain a screening log to record details of all patients screened and to confirm eligibility or record reasons for screening failure, as applicable.

Procedures conducted as part of the patient's routine clinical management (e.g., blood count) and obtained before signing of the ICF may be utilized for screening or baseline purposes provided the procedures met the protocol-specified criteria and were performed within the time frame defined in the SoA.

8.1. Efficacy Assessments

Disease will be assessed by standard criteria as indicated in Section 8.1.1. Evaluations of response will be performed at the time points listed in SoA (Table 1). Additional studies will evaluate leukemic involvement (e.g., imaging/blood/bone marrow, or other tissue samples that are obtained from the patient) as part of SoC. Patient long-term overall survival and PFS will also be evaluated. Efficacy assessments, including CT scans used to assess extramedullary disease may be collected and sent to a central imaging facility for assessment along with any disease assessment reports.

This study will use the ELN recommendations for AML response criteria (Döhner et al, 2017) as well as the FDA guidance for developing AML treatments (FDA, 2020). In addition, levels of any molecular marker or mRNA expression of a protein known to represent minimal residual disease or early relapse (e.g., WT1) may be performed. The response criteria are defined in the following section.

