2.2.2.1. Tumor-associated antigens

TAAs that are overexpressed on malignant cells (e.g., Wilms Tumor-1 [WT1]; Survivin; and the cancer testis antigens [CTAs] Preferentially Expressed Antigen in Melanoma [PRAME] and NY-ESO-1) have been targeted using a range of immunotherapeutic strategies in both the preclinical and clinical setting, including antibody-based therapies, peptide vaccines and adoptive T cell transfer. Table 2 shows the frequency of expression of select TAAs in AML based on published reports (Carter et al, 2012; Almstedt et al, 2010; Cilloni et al, 2002).

Table 2: Frequency of TAAs expressed in AML

	WT1	SURVIVIN	PRAME	NY-ESO-1
AML	70-90%	72-100%	30-60%	0-7%

Abbreviations: AML=Acute Myeloid Leukemia; TAA=tumor-associated antigens; WT1=Wilms Tumor-1

WT1: WT1 is a nuclear zinc finger transcription factor that is essential during embryonic development of the urogenital system. Post-natally, WT1 expression in healthy tissues is limited to the ovary, testis, podocytes of the kidney and the mesothelial linings of the peritoneum and pleura. Additionally, WT1 is expressed at low levels in hematopoietic progenitor cells where it normally acts to induce quiescence of CD34⁺ Lin⁻ cells and promote differentiation of precursors at later stages of development (Harris, et al, 2016; Hohenstein and Hastie, 2006). In contrast, WT1 is highly expressed in several solid tumors, and >70% of AMLs affecting children and adults; high levels of WT1 expression are associated with poor prognosis (Hou et al, 2010). WT1 is also aberrantly expressed in chronic myeloid leukemia and in advanced forms of myelodysplasia (Rosenfeld et al, 2003). In leukemic blasts, the balance of WT1 isoforms expressed appears to promote proliferation and resistance to apoptosis, while inhibition of WT1 expression (e.g., using short hairpin ribonucleic acid) reverses these effects, thereby eliminating leukemic cells with clonogenic potential (Yang et al, 2007; Yamagami et al, 1996).

Survivin: Survivin is a member of the inhibitor of apoptosis protein family and is overexpressed in the majority of tumors including esophageal, lung, ovarian, breast, and colorectal cancer, as well as most hematologic malignancies (Andersen et al, 2007). Elevated Survivin expression is commonly associated with resistance to chemotherapy, enhanced proliferative capacity and, in the case of AML, it is an independent unfavorable prognostic factor (Carter et al, 2012).

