2.2.3. MultiTAA-specific T cells (MT-401)

MT-401 is a non-genetically modified allogeneic multiTAA-specific T cell therapy that is being developed for the treatment of patients with AML after receiving allogeneic stem-cell transplant. MT-401 is composed primarily of multi-antigen specific CD4+ and CD8+ T cells that have been manufactured under current Good Manufacturing Practices (cGMP) by *in vitro* stimulation of T cells with APCs, which were cultured with overlapping peptide pools. Briefly, donor T cells are cultured with APCs presenting peptides spanning the primary sequence of four TAAs, namely, PRAME, NY-ESO-1, Survivin, and WT1 in the presence of recombinant cytokines.

This study was initiated with MT-401 using a manufacturing process that took >2 weeks; however, recently the manufacturing process has been shortened to about one week which is referred to as an accelerated process in the study protocol.

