2.2.4. Choosing the Optimal TAA Targets

The CTAs NY-ESO-1 and PRAME are expressed to varying degrees in leukemic stem cells and blasts (Table 2). In addition, WT1 is expressed in 70-90% of AML cells, while Survivin is ubiquitously expressed on malignant cells. The expression of these tumor antigens in AML and their apparent immunogenicity make them potential targets for T cell therapy (Carter et al, 2012; Almstedt et al, 2010; Cilloni et al, 2002). Although most tumor cells express one or more of these antigens, there may be differences in levels of antigen expression from patient to patient, as well as between individual tumor cells. Thus, in order to provide potential clinical benefit to the majority of patients, T cell lines with simultaneous activity against NY-ESO-1, PRAME, Survivin, and WT1 were generated and the safety of these cells was tested in a dose escalation Phase 1 study. Additionally, the expression frequency of these antigens on tumor cells was assessed, though antigen expression was not an eligibility criterion.

As a means of stimulating T cells, APCs that had been incubated with GMP grade overlapping peptide pools that span the primary sequences of NY-ESO-1, Survivin, WT1 and PRAME are used. These peptide libraries encompass all possible human leukocyte antigen (HLA) class I epitopes and the majority of HLA class II epitopes of each protein. Using this approach T cell lines with specificity for up to four antigens will be generated, as has been the experience in pre-clinical validation studies (Weber et al, 2013) and the ongoing Phase 1 clinical study at Baylor College of Medicine (NCT02494167). Since the individual peptides are at least 15 amino acids in length, activation of both CD4+ and CD8+ T cells is anticipated.

Confidential Page 23 of 74

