Those patients who enter the study prior to HSCT must meet applicable inclusion/exclusion criteria prior to and following HSCT for study entry and must agree to provide bone marrow aspirate sample(s) to be held for testing.

Relapse is defined as bone marrow blasts \geq 5%, or reappearance of blasts in the blood, or development of extramedullary disease, or development of MRD positivity after having a post-treatment MRD negative status.

Confidential Page 29 of 74

Disease assessments, as outlined in the Schedule of Activities (SoA) (Table 1), will be performed by local and central laboratory facilities. Screening assessment for Group 1 patients can be a prior disease assessment completed within 45 days of screening as per SoC. For Group 1, pre-transplant testing of MRD should be performed locally by any testing methodology and results recorded in the eCRF. Post-transplant baseline MRD testing will be performed centrally and results must be available prior to randomization. MRD⁺ will be defined as CR (including normalization of counts) with detection in blood, bone marrow or any other tissues by flow cytometry and/or molecular testing (eg, PCR, next generation sequencing).

The study will evaluate safety and efficacy endpoints in post-HSCT patients after the infusion of MT-401 using standard methods of assessment (peripheral blood and bone marrow evaluation, positron-emission tomography [PET] scan, etc.). Response will be evaluated using the European LeukemiaNet (ELN) recommendations (Döhner et al, 2017). Historical data will inform the clinical relevance of the magnitude and durability of response in Group 2 and will supplement data from the concurrently randomized control arm in Group 1 (Arm B).

The Data Monitoring Committee (DMC; described in Section 9.4) will review data after the first 45 RFS events in Group 1 have been observed (as described in Section 9.4) to assess safety and evaluate estimates of RFS for future study planning. Additionally, the Sponsor will review safety and efficacy data in Group 2 after approximately the first 10 patients per subgroup have progressed or have had the opportunity to be followed for 6 months.

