8.1.1. Disease Assessment - Response Criteria in AML

The response criteria in AML (Döhner et al, 2017) are as follows in Table 6Relapse includes either hematologic and/or molecular relapse as defined in Table 6 at any disease assessment.

Confidential Page 43 of 74

Table 6. Response Criteria in AML

Category	Definition
CR without minimal residual disease $(CR_{MRD}$ -)	If studied pretreatment, CR with negativity for a genetic marker by quantitative reverse transcription polymerase chain reaction (RT-qPCR), or CR with negativity by multiparameter flow cytometry (MFC) and/or molecular testing
Complete remission (CR)	Bone marrow blasts <5%; a bsence of circulating blasts and blasts with Auer rods; a bsence of extramedullary disease; a bsolute neutrophil count \geq 1.0 x 10 $^9/L$ (1000/µL); platelet count \geq 100 x 10 $^9/L$ (100,000/µL) Note: MRD $^+$ or unknown
CR with incomplete recovery (CR _i)	All CR criteria except for residual neutropenia ($<1.0 \times 10^9/L [1000/\mu L]$) or thrombocytopenia ($<100 \times 10^9/L [100,000/\mu L]$)
Morphologic leukemia-free state (MLFS)	Bone marrow blasts <5%; absence of blasts with Auer rods; absence of extramedullary disease; no hematologic recovery required
Partial remission (PR)	All hematologic criteria of CR; decrease of bone marrow blast percentage to 5 to 25 percent; and decrease of pretreatment bone marrow blast percentage by at least 50 percent
Treatment failure	
Primary refractory disease	No CR or CR _i a fter 2 courses of intensive induction treatment; excluding patients with death in a plasia or death due to indeterminate cause
Death in a plasia	Deaths occurring ≥7 days following completion of initial treatment while cytopenic; with an aplastic or hypoplastic bone marrow obtained within 7 days of death, without evidence of persistent leukemia
Death from indeterminate cause	Deaths occurring before completion of therapy, or <7 days following its completion; or deaths occurring ≥7 days following completion of initial therapy with no blasts in the blood, but no bone marrow examination available
Response criteria fo	
Stable disease ^a	Absence of CR _{MRD} -, CR, CR _i , PR, MLFS; and criteria for PD not met

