Phase 2 Active Disease (Group 2):

The statistical methods for analyzing ORR for Group 2 are identical to those described for CR. For Group 2 active disease patients, DOR, PFS and OS will be estimated using the KM product limit method and summarized similar to RFS for Group 1 as described above. For Group 2 patients achieving CR following bridging therapy, RFS and GRFS will also be estimated using the KM product limit method as described above for Group 1.

7.4.6 *Additional Efficacy Endpoint Analysis Methods*

The analysis of markers of immune function, cell targeting, and signaling pathways will not be discussed in this SAP. If analyses of these endpoint are explored, they will be described in a separate analysis plan and may not be included in the primary CSR.

For Group 1 adjuvant patients, the time to MRD⁺ will be summarized similar to RFS, but with no statistical comparisons.

For Group 2 CR patients, the time to MRD⁻ will be summarized descriptively.

For Group 2 Subgroup D, among patients who had PCR detection of MRD at baseline, the percentage reduction from baseline will be summarized, as well as the number and percentage of patients whose disease level reduced by 50% or more.

A summary of PRO data will be presented using descriptive statistics for Group 2 only.

7.4.7 *Statistical/Analytical Issues*

7.4.7.1 *Adjustments for Covariates*

The planned primary analysis models will include adjustments for stratification factors of pre-transplant MRD status and cytogenetic risk. Subgroup analysis and/or analyses including additional factors may be conducted based on, but not limited to, the following covariates:

- Age (18-64 years, 65 years and above)
- Genetic mutations
- Transplant donor type (matched sibling, matched unrelated, haploidentical)
- Conditioning regimen (myeloablative, reduced intensity/nonmyeloablative)
- Complete remission status prior to transplant (CR1, CR2, CR3)

For time to event endpoints forest plots of the event-free rates at landmark times may be generated to display the outcomes in subgroups. Additionally, Kaplan-Meier plots with subgroup KM curves overlaid on the same plot may be presented. For binary endpoints, the rates within subgroups may be presented in forest plots.

Subgroup analyses are described in Section 7.4.7.7. In addition, data may be analyzed post-hoc to explore the effects of various factors. Such analyses will be labeled as post-hoc.

7.4.7.2 *Handling of Dropouts or Missing Data*

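### The plan does not keep WT1, an antigen that MT-401 targets, out of the MRD calls behind Group 1 RFS and Subgroup D CR_MRD-; if WT1 is used for those calls, the result can be biased towards MT-401

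*Protocol*

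**What the plan says.** **Target.** Protocol 2.2.3 describes donor T cells stimulated with peptides spanning the "primary sequence of four TAAs, namely, PRAME, NY-ESO-1, Survivin, and WT1". Protocol 2.2.4 adds that "WT1 is expressed in 70-90% of AML cells", and 2.2.2.1 that "WT1 is expressed at low levels in hematopoietic progenitor cells".

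**Marker.** Protocol 8.1 (Efficacy Assessments) adopts the ELN and FDA response criteria. It then allows further marker testing beyond them: "mRNA expression of a protein known to represent minimal residual disease or early relapse (e.g., WT1) may be performed". For the response definitions it refers to the next section.

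**Definitions.**
- Protocol 4.1 defines MRD+ as CR with detection "by flow cytometry and/or molecular testing (eg, PCR, next generation sequencing").
- Protocol Table 6 lets CR_MRD- be met by "CR with negativity for a genetic marker by quantitative reverse transcription polymerase chain reaction (RT-qPCR"), or alternatively by negativity on flow cytometry and/or molecular testing. SAP Table 2 gives RT-qPCR or flow cytometry.
- Both tables define molecular relapse as MRD returning by RT-qPCR or flow cytometry, if studied before treatment.
- None of these lists markers, sets a threshold or excludes target antigens. Footnote j of the Schedule of Activities sends the reader back to 4.1 for the MRD methods.

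**Use.** Molecular relapse is an RFS event in Group 1 (Protocol 9.3.2; SAP 6.4.1.2). Conversion from MRD+ to MRD- is the Subgroup D primary response (SAP 6.4.1.2). SAP 7.4.6 adds a Subgroup D summary: "among patients who had PCR detection of MRD at baseline, the percentage reduction from baseline will be summarized".

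**Discordant tests.** SAP 7.2 counts a patient as MRD+ if either of two methods detects MRD, but states this only within the definition of the randomized population.

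**The concern.** An endpoint marker should respond to treatment only through the disease it measures. WT1 expression may not meet that standard here, because MT-401 selects against WT1-expressing cells. If a WT1-low clone survives, the WT1 signal can fall or stay low while leukemia persists. Observation patients face no such selection before relapse, so the error would fall in treated patients only.

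Two endpoints are exposed. In Group 1, a molecular relapse in Arm A could be found late while one in Arm B is found on time. In Subgroup D, a WT1-negative result could be scored as CR_MRD-. Table 6 joins its alternatives with an or, so as worded RT-qPCR negativity could suffice while another method is still positive. Duration of CR_MRD-, and duration of CR in Subgroup C after CR_MRD-, also depend on molecular relapse. The study is open-label, and Protocol 9.4 says only that an independent efficacy review committee may be formed.

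**Working it through.** **1. The plan's own figures reproduce.** With 1:1 allocation, the Schoenfeld formula gives events = 4(1.960 + 0.842)² / (ln 0.55)² = 88, against 90 stated. Power at 90 events is Φ(√90/2 × |ln 0.55| − 1.960) = 0.809, against 80% stated. For Protocol Table 7 (n = 30, exact one-sided 0.05), a 20% control rate needs 11 responders, and 80% and 90% power fall at true rates of 42.7% and 46.7% (stated 43% and 47%). A 10% control rate needs 7 responders, with 28.7% and 32.5% (stated 29% and 32%). No stated figure is wrong on this point.

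**2. What is unknown.** The documents do not give the share of patients whose MRD would be followed by WT1, or how often a WT1-low clone would escape the other tests. The shares below are assumptions. If WT1 feeds no endpoint, every excess is zero.

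**3. Group 1 RFS, no true effect.** Assumed: 150 patients accrued uniformly over 50 months, exponential RFS with median 8 months in both arms, log-rank test at the 90th event, and a share q of Arm A events found d months late. The table gives the chance of a two-sided 0.05 result favouring MT-401 (nominal 2.5%), from 4,000 simulated trials per setting. Monte Carlo standard error near the nominal level is √(0.025 × 0.975 / 4000) ≈ 0.25 points, and the simulated value with no delay was 2.8%.

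| | d = 3 months | d = 6 months |
|---|---|---|
| q = 10% | 3.8% | 5.5% |
| q = 20% | 5.3% | 8.8% |

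A separate simulation of the same settings gave 4.0%, 5.1%, 5.1% and 9.0% (in the order 10%/3, 10%/6, 20%/3, 20%/6), with median apparent hazard ratios of 0.97, 0.93, 0.93 and 0.88.

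An outer bound assumes the masked events are never counted, so the apparent hazard ratio is 1 − q. The chance is then Φ(√90/2 × |ln(1 − q)| − 1.960). For q = 10% this is Φ(4.743 × 0.1054 − 1.960) = Φ(−1.460) = 7.2%; for q = 5% it is 4.3% and for q = 20% it is 18.4%. This bound is too harsh, because hematologic relapse and death would still be counted.

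**4. Subgroup D CR_MRD-, true rate equal to the control rate p0.** If a share w of true non-converters is misread as MRD-negative, the apparent rate is p = p0 + (1 − p0)w. False success is P(X ≥ r) for X ~ Bin(30, p).

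| p0 | r | w = 0 | w = 5% | w = 10% |
|---|---|---|---|---|
| 10% | 7 | 2.6% | p = 14.5%: 13.4% | p = 19%: 34.0% |
| 20% | 11 | 2.6% | p = 24%: 8.3% | p = 28%: 19.4% |

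At p0 = 10%, smaller shares of w = 1% and 2% give 3.9% and 5.6%. SAP 7.4.7.5 speaks of a two-sided 0.05 test instead. With an upper tail of 0.025 and p0 = 10%, r becomes 8 and the figures are 0.8% at w = 0, 5.9% at 5% and 19.7% at 10%.

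**The case against.** The strongest reply is that no section makes WT1 decide anything. Protocol 8.1 makes the test optional and additional and then hands over to Table 6, which never names WT1. Whether WT1 over-expression is a genetic marker in Table 6's sense is not stated. MRD status is tested centrally, and the assay may not use WT1 at all. This stands: the point is an omission, not a stated use.

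A reader might infer that any fall in WT1 after MT-401 is an artefact. The documents do not support that. Killing WT1-high leukemia lowers the signal correctly; a false negative needs a surviving WT1-low clone that the other methods also miss or that the or-wording lets pass. A reader might also take Protocol 2.1 as conceding antigen-low escape. That section claims the opposite, that epitope spreading prevents it. This is a hypothesis about the product, and an endpoint should not depend on it. Signal from normal progenitors is weak support: Protocol 2.2.5 reports no myelosuppression in WT1-directed studies, and CR_MRD- requires count recovery.

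Exposure in RFS is also limited. Hematologic relapse and death always count, and molecular relapse applies only to a marker studied before treatment. The 10-20% above is a share of all Arm A events. If, say, half of those were molecular relapses (an assumption), 20-40% of the molecular relapses would have to be delayed.

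Finally, barring WT1 discards WT1-positive results that might show relapse early. That cost is real. But detection by WT1 would differ between arms, and an either-positive rule alone would leave that difference in RFS.

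**Conclusion.** The point holds as a gap in the endpoint definitions. The plan names a target antigen as a possible MRD marker in its efficacy section, and nothing keeps it out of the calls that define Group 1 RFS events and the Subgroup D primary response. If WT1 is used for those calls, bias in favour of MT-401 is possible. The stronger reading, that the endpoints are biased as planned, is not supported.

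The size cannot be computed from the documents. It is zero if WT1 feeds no endpoint. Under the assumptions above, one-sided false success for RFS is about 4-9% against 2.5%. In Subgroup D, with the one-sided exact test and control rates of 20% to 10%, it is about 8-13% at 5% misreading and 19-34% at 10%, against 2.6%. Subgroup D is the more sensitive because it is small and its response is itself an MRD call. The Subgroup C CR rate is unaffected, since CR counts there whatever the MRD status.

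**What to change.** In Protocol 8.1 and Table 6, and in SAP Table 2 and 7.4.6, state that expression of WT1, PRAME, Survivin or NY-ESO-1 is exploratory only. It should not decide MRD+, MRD-, molecular relapse or CR_MRD-, nor enter the Subgroup D percentage-reduction summary, and the rule should be the same in both Group 1 arms. Take these calls from flow cytometry or from leukemia-specific mutation or fusion tests. Extend the SAP 7.2 rule, that a patient is MRD+ if either test detects MRD, to post-baseline assessments, so that the or in Table 6 cannot let one negative test override a positive one.

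The cost is wording in two documents; no sample size or event count changes. The downside is that a patient whose only PCR marker is WT1 would be followed by flow cytometry or sequencing, with possibly later detection. If WT1 was never meant to count, the exploratory-only statement simply records that.
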